RADVAX: A STRATIFIED PHASE II DOSE ESCALATION TRIAL OF STEREOTACTIC BODY RADIOTHERAPY FOLLOWED BY IPILIMUMAB IN METASTATIC MELANOMA

Principal Investigator: [name] MD PhD
University of Washington
Department of Radiation Oncology
[contact]
[contact]
Email: [contact]

Funding Sponsor: Department of Radiation Oncology
University of Washington

Sub-Investigators [name]
[name]
[name]
[name]

Statistician: [name]

Version date: *Protocol Amendment 7: version November 15, 2016
(replacing Protocol Amendment 6: version January 15, 2016)*

CONFIDENTIAL

This material is the property of the sponsor. Do not disclose or use except as authorized in writing by the study sponsor

Printed on 1/31/2017

Table of Contents

STUDY SUMMARY 1

1 INTRODUCTION 2

2 STUDY OBJECTIVES 4

3 STUDY DESIGN..... 4

4 SUBJECT SELECTION AND WITHDRAWAL 6

5 STUDY DRUG..... 7

6 STUDY PROCEDURES 7

7 ASSESSMENT OF TUMOR REPOSE..... 12

8 STATISTICAL PLAN 144

9 SAFETY ASSESSMENT AND ADVERSE EVENT REPORTING 18

10 REGULATORY, QUALITY AND ADMINISTRATIVE REQUIREMENTS..... 22

REFERENCES 23

List of Abbreviations

SBRT: Stereotactic body radiation therapy
 CTLA 4: Cytotoxic t-lymphocyte antigen 4

Study Summary

Title	RADVAX: A STRATIFIED PHASE II DOSE ESCALATION TRIAL OF STEREOTACTIC BODY RADIOTHERAPY FOLLOWED BY IPIILIMUMAB IN METASTATIC MELANOMA
Short Title	RADVAX
Protocol Number	CC IRB # 9031
Phase	Phase II
Methodology	Open Label
Study Duration	3 years
Objectives	
 1. The primary objectives are to determine feasibility and immune-related clinical responses associated with SBRT when given in conjunction with ipilimumab 2. The secondary objectives are to determine late toxicity and immune pharmacodynamic changes after SBRT followed by ipilimumab
Number of Subjects	40
Diagnosis and Main Inclusion Criteria	Patients with previously untreated or previously treated metastatic melanoma with bone, lung, liver, or subcutaneous or nodal involvement but without evidence of active brain involvement. Patients who have previously been treated with radiation will be included in the study, so long as a suitable plan for treatment can be developed.
Study Product, Dose, Route, Regimen	Stereotactic Body Radiation Therapy
Duration of administration	Radiation Treatment to be delivered prior to initiation of ipilimumab
Reference therapy	Ipilimumab
Statistical Methodology	This is a stratified phase II study of escalating fractions of stereotactic body radiotherapy (SBRT) combined with immunotherapy for previously untreated or previously treated metastatic melanoma patients. Phase I was stratified by site: bone or lung vs. liver or s.c. Six patients were enrolled per dose cohort. Phase II is stratified by site: bone or lung vs. liver or s.c. In phase II, 20 patients will be treated at the MTD in each stratum. Descriptive statistics will be generated for both phases of the study.

CONFIDENTIAL

This material is the property of the sponsor. Do not disclose or use except as authorized in writing by the study sponsor

Printed on 1/31/2017

1 Introduction

This document is a protocol for a human research study. This study is to be conducted according to US and international standards of Good Clinical Practice (FDA Title 21 part 312 and International Conference on Harmonization guidelines), applicable government regulations and Institutional research policies and procedures.

1.1 Background

Malignant melanoma is a virulent disease claiming almost 8600 patients annually in the United States.(1) the median survival with metastatic disease is usually less than one year. Systemic therapies are largely ineffective in this disease and there are no approved therapies beyond first line treatment.(2) In 2010 Hodi, et al, published the first phase III randomized trial demonstrating a survival benefit in metastatic melanoma using the immunotherapeutic agent ipilimumab, an anti-CTLA-4 antibody.(3) This was a multi-institutional randomized, double-blind phase III trial in previously treated patients with a diagnosis of unresectable stage III or IV melanoma. Patients were randomized in a 3:1:1 ratio, to treatment with an induction course of ipilimumab, at a dose of 3 mg per kilogram of body weight, plus a gp100 peptide vaccine; ipilimumab plus gp100 placebo; or gp100 plus ipilimumab placebo — all administered once every 3 weeks for four treatments. The median overall survival was 10.0 months among patients receiving ipilimumab plus gp100, as compared with 6.4 months among patients receiving gp100 alone (hazard ratio for death, 0.68; P<0.001). The median overall survival with ipilimumab alone was 10.1 months (hazard ratio for death in the comparison with gp100 alone, 0.66; P = 0.003). No difference in overall survival was detected between the ipilimumab groups (hazard ratio with ipilimumab plus gp100, 1.04; P = 0.76). Grade 3 or 4 immune-related adverse events occurred in 10 to 15% of patients treated with ipilimumab and in 3% treated with gp100 alone. The best overall response rate was 5.7% and 10.9% in the two ipilimumab arms. Although these results are promising, the fact that only approximately 10% of patients responded to ipilimumab suggests that this strategy is not effective for all patients with metastatic disease.

Mechanism of action of ipilimumab and relevance for melanoma

T lymphocytes are prime mediators of tumor immuno-surveillance, particularly for patients with melanoma in whom T cell infiltration into tumors predicts clinical outcome and for whom immunotherapeutic strategies have in some cases shown clinical utility. In the course of interactions between antigen presenting cells (APC) and T cells, surface expression of the co-stimulatory molecules CD80 and CD86 is upregulated. Initially, CD80/86 ligates and activates CD28 which is constitutively expressed on T-cells resulting in their activation. Cytotoxic T-lymphocyte antigen-4 (CTLA-4; CD152) is a cell-surface receptor that is expressed (within approximately 72 hours *in vitro*) on T-lymphocytes in response to their activation by interaction with APCs or pharmacologic stimulation of the T-cell receptor. CTLA4 has a substantially higher affinity for CD80 and CD86 than CD28; its activation down-modulates T-cell proliferation and cytokine secretion, effectively limiting the immune reactivity directed against a given antigen stimulus. Therefore, inhibition of CD80/86 binding to CTLA4 is a potential strategy to prevent down-regulation of the immune response. Ipilimumab, a fully human monoclonal antibody (IgG1) blocks CTLA-4 and has been shown to promote antitumor immunity in patients with metastatic melanoma and was approved for use by the FDA in March 2011 for patients with metastatic melanoma.(4) The effectiveness of this strategy is predicated upon T-lymphocyte activation through interaction with the APC to have occurred. CTLA-4 blockade can then prevent the down-regulation of the anti-tumor immune response. The development of novel strategies that successfully “vaccinate” patients to their melanoma prior to the delivery of CTLA-4 are important area clinical research.

CONFIDENTIAL

This material is the property of the study sponsor. Do not disclose or use except as authorized in writing by the study sponsor

Printed on 1/31/2017

Stereotactic Body Radiation Therapy (SBRT)

Stereotactic body radiotherapy (SBRT) is a highly precise treatment technique that delivers large tumoricidal doses of radiation to a small tumor. Although this represents one of the most exciting and active frontiers of research in the radiotherapeutic management of early stage NSCLC, this treatment technique was originally developed in 1951 by a Swedish neurosurgeon, Lars Leksell for the treatment of intracranial metastases.(5) SBRT allows for escalation of dose without extending the overall treatment duration, as would be the case with conventional fractionated radiotherapy. A Phase I dose-escalation trial evaluated patients with T1-2 N0 NSCLC with no restriction on tumor location. Each treatment course was administered over 3 fractions with a starting dose of 8 Gy per fraction. Patients were stratified into 3 dose-escalation groups based on T stage and size (T1, T2 <5 cm, and T2 5–7 cm). This trial demonstrated that the maximally tolerated dose for T2 tumors larger than 5 cm was 22 Gy × 3 for, and was not reached at 20 Gy × 3 for T1 tumors or at 22 Gy × 3 for T2 tumors smaller than 5 cm.(6). There were a total of 10 local failures in the 47 patients treated in this study with nine local failures in patients treated to the lower dose levels (<16Gy x 3). A Phase II trial from the same group of investigators treated 70 patients with Stage I NSCLC with the doses established in the phase I study. With a median follow-up of 17.5 months, the local control was 95%, which appears at least as effective as a definitive surgical resection. Severe toxicity occurred at a median of 10.5 months in 17% of those patients with peripheral lesions versus 46% with central lesions.(7) Several other institutions have subsequently published their experience utilizing SBRT for early lung cancer with a variety of dose fractionation and prescription schemes. The initial data appear promising with 80%–100% local control, 40%–100% 2- to 3-year survival, and 0%–4% grade 3 toxicity), although in general the median follow-up for these studies is relatively short.(8-14). Given these promising results, the RTOG (RTOG 0618) has initiated a phase II study of stereotactic body radiotherapy for operable patients with early stage operable NSCLC. Additionally, [name] initiated a randomized trial of surgical resection vs. stereotactic body radiation for early stage lung cancer in early 2010 (RTOG 1021). While the results of these studies are eagerly anticipated, the ability to treat early stage lung cancer with SBRT is rapidly being incorporated into most Radiation Oncology facilities here in the United States.

SBRT in the setting of metastatic disease

SBRT is being used increasingly in the setting of metastatic disease. Initially, it was integrated as an ablative approach with a goal of tumor sterilization in oligometastatic disease with minimal morbidity and good long-term clinical outcome in these highly selected patients.(15-17) Subsequently, data have emerged that SBRT provides effective palliation in the metastatic setting for palliation of bone, lung, liver, and subcutaneous/nodal metastases with minimal morbidity.(15, 16, 18-20) As such, SBRT is being increasingly utilized in the metastatic setting for palliative intent.

SBRT and Immune Activation

There is emerging evidence that hypofractionated radiotherapy is immunostimulatory. In a recently published study in *Blood*, Lee et al demonstrated that the therapeutic effect with ablative hypofractionated radiotherapy was dependent upon activation of CD8+ T-lymphocytes.(21) Additionally, there are pre-clinical data to suggest that CTLA-4 blockade along with ablative radiotherapy to an index lesion can prevent metastatic dissemination of disease.(22, 23) Finally, there are clinical data to suggest that SBRT provides greater local control and a reduction in regional and distant dissemination of disease when compared with surgery alone in NSCLC. One hypothesis to explain these surprising data is that the

CONFIDENTIAL

This material is the property of the study sponsor. Do not disclose or use except as authorized in writing by the study sponsor

Printed on 1/31/2017

immunostimulatory effect of SBRT results in improved control of disease and prevention of spread.(24)

Summary

We propose a stratified phase I/II clinical trial of SBRT to an isolated index lesion followed by ipilimumab in patients with previously untreated or previously treated metastatic melanoma in patients eligible for CTLA-4 blockade. In our protocol, the goal is to “vaccinate” patients against their melanoma via SBRT and then to elaborate the induced immune response with the FDA-approved CTLA-4 blocking antibody ipilimumab.

2 Study Objectives

The overall objective of the study is to determine the feasibility of delivery of SBRT to an index lesion in patients with metastatic melanoma prior to standard of care immunotherapy with ipilimumab.

Primary Objective

The primary objectives are to determine feasibility and immune-related clinical responses associated with SBRT when given in conjunction with ipilimumab.

Secondary Objective

[figure not shown]
The secondary objectives are to determine late toxicity and immune pharmacodynamic changes after SBRT followed by ipilimumab.

3 Study Design

3.1 General Design

This is a stratified phase II study of escalating fractions of stereotactic body radiotherapy (SBRT) combined with immunotherapy for previously untreated or previously treated metastatic melanoma patients. Patients will undergo a short course of high dose SBRT to a single index lesion that measures 1 cm to 5 cm. These fractions will be administered several days apart. Radiotherapy will be immediately followed by ipilimumab, at the FDA-approved dose and schedule.

RADVAX TRIAL

Study Duration: The expected accrual rate = 15 pts/yr. The protocol is designed for a maximum total of 40 patients. The expected total study duration is 3 to 3 ½ yrs needed to complete both phases, allowing for suspensions for interim analyses.

*Study Enrollment is intended to mean consultation

3.2 Primary Study Endpoints

Late toxicity is defined generally as an adverse event associated with the treatment which occurs beyond 30 days after last injection of ipilimumab (i.e., adverse events which are observed months after treatment are most likely associated with SBRT) and is defined more precisely in Section 5.2.

Clinical response will be scored on a non-index lesion or lesions using immune-related response criteria (irRC). Immune-related progression-free survival (irPFS) is defined as the time from first day of radiotherapy to first documented irPD, death due to any cause or last patient contact alive. Immune pharmacodynamic changes will be examined, as described in Section 7.22.(25) Overall immune response is defined as >2-fold pre-treatment/post-treatment increase in any of the key T cell parameters.

CONFIDENTIAL

This material is the property of the study sponsor. Do not disclose or use except as authorized in writing by the study sponsor

Printed on 1/31/2017

4 Subject Selection and Withdrawal

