4.4.2 Data Collection and Follow-up for Withdrawn Subjects

Every effort will be made to follow subjects off study for toxicity, disease progression and survival.

5 Study Drug

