5.2 Dose Limiting Toxicities Definitions

Dose-limiting (Acute) Toxicity is defined as any treatment related Grade 4 or higher immune-related toxicity or Grade 3 or higher non-immune related toxicity which is observed during treatment or within 30 days of the final ipilimumab injection **and** which is probably or definitely related to radiation treatment. This definition will be used for de-escalation to the -1 dose level. All toxicities will be graded by NCI CTC Version 4.0.

Late toxicity Late toxicities will be graded according to the RTOG/EORTC late morbidity scoring system. The time frame for late toxicity is open-ended and late toxicities have been known to occur a year or more after therapy. Follow-up for late toxicity will cease when a patient experiences disease progression, since 2nd line therapies may then be initiated.

Non immune-related toxicity (SBRT-related toxicity) is defined as any toxicity observed within the tissues contained within the radiation portal and is consistent with tissue reaction to radiation exposure at any time during follow-up.

Immune-related toxicity is defined as an adverse event that is associated with exposure to ipilimumab and that is consistent with an immune phenomenon.

CONFIDENTIAL

This material is the property of the study sponsor. Do not disclose or use except as authorized in writing by the study sponsor

Printed on 1/31/2017

6 Study Procedures

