6.3 Ipilimumab Administration

Ipilimumab will be given in the outpatient setting. Patients will receive ipilimumab at 3 mg/kg i.v. delivered as per the package insert every 3 weeks (+/- 2 days) for treatments. Patients will be monitored in the clinic after the infusion and discharged when deemed stable by the clinical staff. Medications to treat hypersensitivity reactions should be immediately available, and may include epinephrine, diphenhydramine, methylprednisolone and nebulized albuterol.

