6.5 Study Calendar

	Eligibility/Pre-Treatment	Post-SBRT; Pre- Ipi	Ipilimumab Clinic Visits	EOS visit
Tests and Observations				
History and PE	X		X	X(as per

CONFIDENTIAL

This material is the property of the study sponsor. Do not disclose or use except as authorized in writing by the study sponsor

Printed on 1/31/2017

				standard of care, usually within 60 days of final ipilimumab infusion)
ECOG score	X		X	X
Radiographic imaging appropriate for ir-RECIST 1.1 criteria (should be the same modality at baseline and EOS) ^b	X			X(as per standard of care, usually within 60 days of final ipilimumab infusion)
Biopsy	X			X ^C
Laboratory				
CBC w/diff, Hgb, Platelets... ^b	X	X ^d	X ^d	
CMP ^b	X	X ^d	X ^d	
Pregnancy Test	X ^a			
Toxicity Assessment	X	X	X	X
Immune studies (Eight 8.5 ml yellow top tubes and one 10 ml SST tube)	X	X ^d	X ^d	x

X^a- Required for women of childbearing potential. If pre-treatment is 30 days from eligibility, you should repeat a pregnancy test within 24 hours of treatment initiation.

X^b- Measurements cannot be more than 60 days from the beginning of treatment.

X^C- As clinically indicated, tumor blocks and/or slides from EOS biopsy or surgery will be collected on all patients.

X^d- The post-SBRT; pre-Ipi Ipilimumab #1 Immune studies and routine clinic blood draw may be combined if last SBRT and the first injection of Ipilimumab will occur within 5 days of each other.

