6.6 Post-treatment Evaluation and follow-up

Patients will be evaluated per standard of care, usually within 60 days after last ipilimumab treatment (End of Study visit, EOS) to determine feasibility and safety (acute toxicity) for the initial phase of the study. Follow-up imaging appropriate for ir-RECIST 1.1 criteria will be obtained within 60 days of the final dose of ipilimumab for restaging. The same imaging modality should be used at follow-up as at baseline. Specimens for immune correlates will also be drawn at this visit. Patients will then be referred to the referring physician for subsequent follow up, according to standard of care. Every effort will be made to obtain records of patients during this follow up, and permission will be sought for the investigators and/or study team to re-contact the patient directly with regard to health status and toxicity.

CONFIDENTIAL

This material is the property of the study sponsor. Do not disclose or use except as authorized in writing by the study sponsor

Printed on 1/31/2017

7 Assessment of Tumor Response

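### irPFS is followed to last contact, but no scan is scheduled after the end-of-study visit, so six-month irPFS tends to be overstated to the extent that later progression is missed

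*Combined protocol and SAP*

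**What the plan says.** Section 3.2 defines irPFS as "the time from first day of radiotherapy to first documented irPD, death due to any cause or last patient contact alive". Section 8.5 uses Kaplan-Meier, so last contact has to be read as the censoring date.

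The Study Calendar (6.5) lists imaging at baseline and EOS only. It times the EOS column as "standard of care, usually within 60 days of final ipilimumab infusion". Section 6.6 is firmer: "Follow-up imaging appropriate for ir-RECIST 1.1 criteria will be obtained within 60 days of the final dose of ipilimumab for restaging". Patients then return to the referring physician, with no scan interval stated.

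The plan does mean to learn of later progression. Section 6.6 says "Every effort will be made to obtain records of patients during this follow up", and 4.4.2 says of withdrawn patients "Every effort will be made to follow subjects off study for toxicity, disease progression and survival". Section 5.2 says "Follow-up for late toxicity will cease when a patient experiences disease progression", which presupposes that progression is known. Section 7.1.1 also allows investigator-assessed clinical benefit.

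Section 8.2 lists the six-month irPFS rate as a primary quantity for each stratum. Section 8.5 says that the estimate and its interval feed into decisions, and cites a historical six-month PFS of about 25% with ipilimumab alone. The Study Summary and Section 2 name only feasibility and immune-related clinical response as primary.

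**The concern.** Knowing that a patient is alive is not knowing that the disease has not progressed. Under 3.2, a patient without a documented event stays at risk until last contact, whether or not the tumour was looked at. After EOS the protocol requires no look before month 6. Sections 3.2 and 8.5 do not say how later scans or clinical progression enter the six-month rate, or what happens when neither exists.

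At stake is a six-month figure that appears to rest on disease status at six months when, for some patients, status was last known a month or more earlier.

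**Working it through.** The plan states no EOS month and no precision figure for irPFS, so there is no figure of its own to reproduce.

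**1. When the EOS scan falls**

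- Three fractions several days apart (3.1, 6.2.3): assumed 4 to 14 days from first to last.
- Ipilimumab immediately afterwards (3.1): assumed 1 to 5 days.
- Four doses (8.4.1 refers to a fourth or final injection; 6.3 leaves the number blank), three weeks apart: 3 × 21 = 63 days, plus up to 3 × 2 = 6 days of tolerance.
- Scan at the 60-day limit (6.6).

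Shortest: 4 + 1 + 63 + 60 = 128 days (4.2 months). Longest: 14 + 5 + 63 + 6 + 60 = 148 days (4.9 months). Month 6 is day 183, so 35 to 55 days before it have no protocol scan. A scan 21 days after the last dose would fall at 4 + 1 + 63 + 21 = 89 days (2.9 months), and fewer doses also widen the gap. To reach month 6, the scan would have to be about 95 to 115 days after the last dose.

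**2. What the definition does in that gap**

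Take a patient who progresses on day 160, is not re-imaged, and is contacted alive on day 250. Under 3.2 no event is recorded by day 183, so the patient counts as a six-month success. Progression before EOS but dated at the EOS scan does no harm, because EOS precedes month 6.

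**3. Size**

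Assumptions: exponential times; true six-month irPFS 25% and 12-month OS 45% (the historical values in 8.5, used only as an example); 10% of irPFS events are deaths without progression; all deaths are captured; a share c of post-EOS progression is captured.

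- Total hazard: λ = ln(4)/6 = 0.2310 per month. Progression hazard: λp = 0.9 × 0.2310 = 0.2079.
- Post-progression death hazard μ solves e^(−12λ) + [λp/(λ−μ)] × [e^(−12μ) − e^(−12λ)] = 0.45. This gives μ = 0.0970; check: 0.0625 + 1.551 × (0.3124 − 0.0625) = 0.450.
- Share progressing between EOS (month e) and month 6 and still alive at month 6: A(e) = 1.551 × [e^(−λe) × e^(−μ(6−e)) − 0.25].
- A(4.3) = 1.551 × (0.3703 × 0.8480 − 0.25) = 0.099. A(4.9) = 1.551 × (0.3223 × 0.8988 − 0.25) = 0.062.
- Expected estimate under 3.2: 0.25 + (1 − c) × A(e).

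| Post-EOS progression captured | EOS at 4.3 months | EOS at 4.9 months | Excess (points) |
|---|---|---|---|
| 0% (deaths only) | 34.9% | 31.2% | 6–10 |
| 50% | 30.0% | 28.1% | 3–5 |
| 80% | 27.0% | 26.2% | 1–2 |
| 100% | 25.0% | 25.0% | 0 |

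Simulations with the hazard of death without progression varied from 0 to 0.04 per month gave 31–36%, 28–31% and 26–27% for the first three rows. If not even deaths were recorded after EOS, the estimate would be 0.25^(e/6), that is 37% and 32%.

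**4. The other direction**

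Suppose all progression is documented, but 25% of patients progression-free at month 6 were last contacted at 4.5 months. The 3.2 rule then gives about 20–23% by simulation.

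**5. Would a new censoring date alone cure it?**

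No. Simulated with censoring at the last assessment, deaths kept as events and no later scans, the estimate was 15–23% with 7 months of follow-up, 28–34% with 12 and 31–36% with 36, against a true 25%. It drifts with follow-up length and at 36 months matches the last-contact rule. Only capture of disease status near month 6 brings the estimate back to 25%.

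**The case against.** The strongest reply is that the large figures pair complete capture of deaths with no capture of progression. Records that give vital status usually also show progression, and 4.4.2, 5.2 and 6.6 all seek it. At 80% capture the excess is only 1–2 points. A patient never reached after EOS is censored near the EOS scan under either rule. The bias needs contact that yields vital status without disease status.

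Second, no irPFS threshold or test is set. For 5 of 20 patients the exact 95% interval is 8.7–49.1%, and a shift of a few points sits well inside it. Both replies stand. They limit the size and severity, but they do not supply the missing rule.

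Third, a stricter repair can do harm. Also censoring deaths that occur long after the last assessment lowers bias if scans are random. With 20 patients and half scanned, however, simulated root mean squared error was 0.115 against 0.110 under 3.2. When scans were symptom-driven (captured in 70% of progressed and 30% of progression-free patients) it was about 0.13 against 0.10. Such a rule also discards observed deaths. This stands, and the fix below avoids it as the main definition.

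Two stronger readings are tempting. A reader might infer that later progression will simply be ignored; the best-effort provisions contradict that. A reader might also infer that the trial will look better than the historical 25% through this artefact. The documents do not give that study's assessment schedule or censoring rule, so the effect on that comparison is unknown.

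**Conclusion.** The point holds in conditional form. That 3.2 follows irPFS to last contact, and that nothing is scheduled after EOS, comes straight from the text. The upward tendency follows to the extent that post-EOS progression is not captured, and the amount captured cannot be known in advance. The 1–2, 3–5 and 6–10 point figures rest on exponential times, a true rate of 25%, complete death capture, four doses and an EOS scan at 4.3–4.9 months. Selective loss of contact could offset or reverse them. The text does not support saying that the estimate will certainly be inflated, or that the trial's conclusions fail. What is affected is a descriptive estimate that 8.2 calls primary and 8.5 uses for decisions. It should be fixed before analysis, so that the convention is not chosen after results are seen.

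**What to change.** 1. In 3.2, define irPFS as time from first radiotherapy to documented irPD or death from any cause, with event-free patients censored at the last evaluable tumour assessment. Keep all observed deaths as events, and keep last-contact censoring for OS only.
2. In 8.5, state a window around month 6. From the records 6.6 already seeks, abstract dates and results of standard-of-care scans and documented clinical progression up to that window, and count them in the six-month rate. This step is essential, because step 1 alone does not remove the bias.
3. For each analysed group (the strata of 8.2, and the previously untreated and previously treated groups of 8.5), report the number with disease status known in the window. Show the last-assessment and last-contact estimates side by side, and say that the six-month rate is not reliably estimable where few patients are assessed.

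A rule that censors deaths long after the last assessment should be a sensitivity analysis at most.

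Cost: a short revision of 3.2 and 8.5 and some record abstraction, with no added scans and no change to treatment. The downside is fewer patients at risk at month 6 and a wider interval. As a guide to scale, the stricter death-censoring variant with 20 patients and half scanned left about 3.5 rather than 6.6 at risk and raised the standard deviation from 0.099 to 0.111.
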